**Intercurrent Events (ICEs) and Corresponding Strategies (Refer to Table 2):**

**Table 2: ICEs and Their Corresponding Strategies**

ICEs	Strategy for Addressing Intercurrent Events
1. Discontinuation of treatment due to lack of efficacy, or due to an AE of worsening of psoriasis. 2. Initiation of other medication or therapy that could improve psoriasis (see Appendix 6.7).	Composite Strategy: The occurrence of these ICEs is captured in the variable definition as patients with these ICEs are considered non-responders.
3. Discontinuation of treatment for other reasons than ICE 1	Treatment Policy: Strategy targeting the effect of treatment assignment, regardless of the occurrence of this ICE.

Note: For patients experiencing multiple ICEs, ICE 2 will override ICE 3 and the composite strategy will be applied.

**Population Level Summary:** Difference in proportions between JNJ-77242113 and placebo.

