### **Continuous Endpoints**

The analysis strategies for ICEs:

- Participants experiencing ICEs 1, 2 and 4 (only apply to Week 52 endpoints after retreatment among adult participants) will be handled with composite strategy and data will be imputed with a zero change (or zero improvement) from baseline from that point onward.
- Participants experiencing ICE 3 will be handled by the treatment policy strategy and observed data will be used regardless of intercurrent events. For participants experiencing multiple ICEs, ICEs 2 and 4 will override an ICE 3.
- Missing data will not be imputed after applying the rules for ICEs. Missing data will be accounted for through correlation of repeated measures in the MMRM model.

For repeated measure continuous endpoints, treatment comparisons will be performed using a MMRM model. The MMRM will include treatment, age group, baseline weight, geographic region and baseline value, as explanatory factors, if applicable. The MMRM model will also include visit, treatment group by visit, and baseline value by visit interaction as additional explanatory factors. An unrestricted (UN) variance-covariance matrix for repeated measures within a participant will be used. If the model with unstructured covariance structure does not converge, alternative covariance structures will be tried in the following order, with the first structure that converges being used in the analysis: heterogeneous Toeplitz, standard Toeplitz, and autoregressive of order 1. The LS mean estimates and their corresponding 95% CI will be provided at each timepoint. In addition, the estimates of LS mean difference and 95% CIs between treatment groups will be provided.

Analysis of covariance will be used to analyze some continuous endpoints when appropriate. The ANCOVA will include treatment group, baseline value, baseline weight, geographic region and age group. The LS mean estimates and their corresponding 95% CI will be provided. In addition, LS mean difference and 95% CIs between treatment groups will be provided.

The analysis of time to loss of IGA 0 or 1 response will be performed in the same manner as the key secondary analyses of time to loss of PASI responses (refer to section 4.3.1.2.1) with the same data handling rule for ICEs and missing data.

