### **4.4.2. Analysis Methods**

In general, the efficacy analyses for exploratory endpoints will be based on FAS or randomized at Week 24 analysis set (Section 4.1). Simple descriptive summary statistics, such as n, mean, SD, median, interquartile range, minimum, and maximum for continuous variables, and counts and percentages for discrete variables will be summarized by study intervention group.

Unless otherwise specified, the treatment comparisons will be performed using the same analysis methods described in Section 4.3.2.3 for other secondary endpoints. The analysis strategy for ICEs and missing data will be handled in the same manner as other secondary analyses (section 4.3.2.3). No adjustments for multiple comparisons will be made for exploratory endpoints.

Additionally, graphical data displays may also be used to summarize the over time data if applicable.

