#### **4.4.2.1. Analyses Through Week 24**

Efficacy analyses at Week 16 and over time through Week 24 will be summarized by randomized treatment group at Week 0.

- **Placebo:** participants randomized to the placebo group at Week 0

For over time summaries at Week 20 and Week 24, only participants who crossed over to receive JNJ-77242113 treatment will be included in the placebo cross over group.

- **JNJ-77242113:** participants randomized to the JNJ-77242113 treatment group at Week 0

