#### **Retreatment period**

To evaluate the efficacy of retreatment after relapse with JNJ-77242113, efficacy data at and after retreatment relative to the time of retreatment (i.e., at the time of retreatment, 4 weeks after retreatment, 8 weeks after retreatment) will be summarized for adult participants who were randomized to placebo at Week 24, were withdrawn from study agent at Week 24, experienced a loss of at least 50% of the Week 24 PASI improvement, and were retreated with JNJ-77242113. Selected endpoints will be summarized at scheduled visits after retreatment.

Participants experiencing ICEs 1-3 after retreatment will be handled in the same manner as the other secondary analyses (section 4.3.2.3) regardless of ICEs occurred prior to retreatment.

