#### **4.4.2.3. Analyses Through Week 52 – Non-randomized JNJ-77242113 Treatment**

For participants who were not randomized at Week 24, efficacy data will be summarized over time from Week 24 through Week 52 in following treatment groups.

- **Placebo-> JNJ-77242113 (adults and adolescents):** participants randomized to placebo group at Week 0 and crossed over to receive JNJ-77242113 at or after Week 16
- **JNJ-77242113 (adult non-responders):** adult participants randomized to JNJ-77242113 treatment group at Week 0 who were both PASI 75 and IGA 0 or 1 non-responders at Week 24, and did not undergo randomization at Week 24

To evaluate efficacy of JNJ-77242113 in adolescent participants, efficacy data will be summarized from Week 0 through Week 52.

- **JNJ-77242113 (adolescents):** adolescent participants randomized to JNJ-77242113 treatment group at Week 0.

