#### 4.4.2.5. Analyses Related to PASI

##### Through Week 24

- The change and percent change from baseline in PASI total score will be summarized over time through Week 24 by treatment group.
- The proportions of PASI responses (PASI 75, PASI 90, and PASI 100) will be summarized over time through Week 24 by treatment group.
- The proportions of participants achieving  $\geq 75\%$  improvement,  $\geq 90\%$  improvement, or achieving 100% improvement from baseline in PASI disease component (Induration, Erythema, and Scaling) and region component (head, trunk, upper extremities, and lower extremities) at Week 16 will be summarized by treatment group.

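### Zero-change imputation after other psoriasis therapy on placebo is not reset at the Week 16 crossover, which can pull down exploratory continuous summaries of JNJ-77242113

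*SAP*

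**What the plan says.** SAP 4.3.2.3 (Continuous Endpoints) handles ICEs 1 and 2 by a composite strategy: "data will be imputed with a zero change (or zero improvement) from baseline from that point onward". SAP Table 2 defines ICE 2 as starting another medication or therapy that could improve psoriasis, and gives no end date.

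SAP 4.4.2 carries this into the exploratory analyses: "The analysis strategy for ICEs and missing data will be handled in the same manner as other secondary analyses".

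Two of those analyses contain crossed-over placebo participants:

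- SAP 4.4.2.1, Weeks 20 and 24: "only participants who crossed over to receive JNJ-77242113 treatment will be included in the placebo cross over group".
- SAP 4.4.2.3, Weeks 24 to 52, where the Placebo to JNJ-77242113 group is defined as "participants randomized to placebo group at Week 0 and crossed over to receive JNJ-77242113 at or after Week 16".

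The outcomes include continuous ones. SAP 4.4.2.5 states: "The change and percent change from baseline in PASI total score will be summarized over time through Week 24 by treatment group". It plans the same PASI summaries for the non-randomized groups through Week 52.

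At retreatment, SAP 4.4.2.2 handles new ICEs "regardless of ICEs occurred prior to retreatment". No such clause appears for the Week 16 crossover.

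**The concern.** The post-crossover curve is meant to show what happens when JNJ-77242113 is started at Week 16. Under the rule as written, therapy started while the participant was on placebo fixes that participant's continuous outcome at zero change for every later visit through Week 52. An event that preceded the first dose of drug is then counted against the drug. The error runs in one direction, towards a smaller improvement.

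**Working it through.** The plan states no figure on this point, so the check traces the rule and then sizes it under stated assumptions.

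**1. Can the case occur?** Protocol 7.1.3 lists the start of prohibited therapy that affects psoriasis evaluations among the reasons for permanent discontinuation, but leaves it to the medical monitor's discretion. Protocol 6.9 says only that the participant may be required to stop. A placebo participant with ICE 2 can therefore remain on study intervention and cross over. ICE 1 matters little here, because those who stopped placebo would generally not cross over.

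**2. How the SAP treats each change of treatment or analysis period**

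| Change | SAP section | ICE window |
|---|---|---|
| Week 16 crossover | 4.4.2.1, 4.4.2.3 | No restart stated |
| Week 24 re-randomization, over-time summaries | 4.4.2.2 | ICEs 1, 2 and 4 between Weeks 24 and 52 |
| Week 24 re-randomization, Week 52 binary key secondary endpoints | 4.3.1.3.1 | ICE 2 from Week 24 to 52, whether or not one occurred earlier |
| Retreatment | 4.4.2.2 | Earlier ICEs disregarded |
| Week 64 onward | 4.4.2.4 | Only ICE 1 applied |

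The safety section (SAP 4.5) also starts at crossover for this group: the Week 52 summary counts only events at or after Week 16. From Week 64 the affected participants' measured scores are used again, so the group's series changes rule between Weeks 52 and 64.

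**3. Binary endpoints.** SAP 4.3.2.3 refers binary endpoints to the key secondary rule in 4.3.1.3.1. That rule makes participants with ICE 2 non-responders but gives no duration. Carry-over past Week 16 is neither stated nor excluded.

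**4. Size for continuous endpoints.** Let f be the fraction of the crossover group with ICE 2 before Week 16, and m the mean improvement if all measured scores were used. If affected participants respond like the rest, then

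reported mean = (1 - f) × m + f × 0 = (1 - f) × m.

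The planned placebo arm is 200 (SAP section 5); the number crossing over would be somewhat lower. Neither f nor m is in the documents; both are assumptions.

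| f | Participants of 200 | m = 60% | m = 70% | m = 80% |
|---|---|---|---|---|
| 0% | 0 | 60.0 | 70.0 | 80.0 |
| 1% | 2 | 59.4 | 69.3 | 79.2 |
| 2% | 4 | 58.8 | 68.6 | 78.4 |
| 3% | 6 | 58.2 | 67.9 | 77.6 |
| 5% | 10 | 57.0 | 66.5 | 76.0 |
| 10% | 20 | 54.0 | 63.0 | 72.0 |

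The adolescent summaries through Week 52 (SAP 4.4.2.13 and 4.4.2.14) are more sensitive to a single case. With 60 adolescents randomized 2:1, about 60 × 1/3 = 20 are on placebo, so one affected participant gives f = 1/20 = 5%.

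**The case against.** Several objections have force.

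- **Reach.** Only exploratory summaries are touched. The co-primary, key secondary and other Week 16 comparisons use no post-crossover data, and the re-randomized comparison has its own ICE window. This stands.
- **Number affected.** Some participants with ICE 2 will be taken off study intervention and never enter the crossover group. This stands: f could be near zero.
- **Conservatism.** The present rule errs against the drug, while a plain restart could err in its favour by crediting JNJ-77242113 with the residual effect of a therapy stopped just before crossover. The protocol recognises such effects: Protocol 5.2 restricts biologics for 12 weeks or 5 half-lives, other systemic therapy and phototherapy for 4 weeks, and topicals for 2 weeks before first dose. This stands and shapes the fix. It does not justify zero change through Week 52 for someone who used a topical briefly in the placebo period.

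A reader might go further and infer that these participants are also non-responders at every visit from Week 20 to Week 52. At an on-drug PASI 75 rate of 75%, f = 2% to 5% would then understate response by 1.5 to 3.75 points. The documents do not support this. The carry-forward wording appears only for continuous endpoints. The 75% is a planning assumption for adults on JNJ-77242113 since Week 0, used for the Week 24 re-randomization. It says nothing about Week 20, when a participant crossing over at Week 16 has had about 4 weeks of drug.

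**Conclusion.** The point holds for continuous endpoints: the stated rule, read with its cross-reference, records zero change on JNJ-77242113 for a placebo-period ICE 2, from Week 20 through Week 52. For binary endpoints the finding is a missing duration. The contrast with re-randomization, retreatment and the safety summary suggests an omission.

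The effect is a relative shrinkage of f in the crossover group's mean change: 1.4 to 3.5 percentage points (70 - 68.6 and 70 - 66.5) at an assumed 70% mean PASI improvement and f of 2% to 5%, and nothing if f is zero. This assumes that affected participants respond like the others; the model-based means would follow it approximately. No confirmatory result depends on it. It is a minor point, worth correcting because the correction is cheap.

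**What to change.** In SAP 4.4.2.1 and 4.4.2.3, for continuous and binary endpoints alike, state that for visits after Week 16 in the Placebo to JNJ-77242113 group, ICEs are counted from the first JNJ-77242113 dose regardless of earlier ICEs, as is already done for retreatment. For this analysis only, still treat as ICE 2 any therapy that is ongoing at crossover, or that was stopped before that dose within the restriction period Protocol 5.2 sets for its class.

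The cost is a short SAP addition and a small extra derivation. Because SAP Table 2 defines ICE 2 by initiation, the derivation also needs stop dates and therapy class. Some residual benefit of an earlier therapy may still be credited to the drug.

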6.3. Assignment to Study Intervention

Central randomization will be implemented in conducting this study. Participants will be assigned to 1 of 2 intervention groups with a 2:1 randomization ratio to JNJ-77242113 or placebo, based on a computer-generated randomization schedule prepared before the study or under the supervision

of the sponsor. Permuted block randomization with stratification by age group (adolescents <18 years and adults ≥ 18 years), baseline weight category for adults only (≤ 90 kg, >90 kg) and geographic region will be used. The IWRS will assign a unique intervention code, which will dictate the intervention assignment and matching study intervention kit for the participant. The requestor must use his or her own user identification and personal identification number when contacting the IWRS and will then give the relevant participant details to uniquely identify the participant.

At Week 24, adult participants randomized to JNJ-77242113 200 mg once daily and who are PASI 75 responders or IGA 0 or 1 responders (ie, those who achieve an IGA score of 0 or 1 and have ≥ 2 -grade improvement from baseline) will be re-randomized using the IWRS either to placebo or JNJ-77242113 200 mg once daily in a 1:1 ratio. Participants will be assigned to treatment groups using permuted block randomization and the randomization will be stratified by geographic region and PASI 90 response status at Week 24.

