9.3.1. General Considerations

Simple descriptive summary statistics, such as n, mean, SD, median, interquartile range, minimum, and maximum for continuous variables, and counts and percentages for discrete variables will be used to summarize most data.

For binary endpoints, treatment comparisons will be performed using a CMH test stratified by age group at screening (adolescents <18 years and adults ≥18 years), baseline weight category for adults (≤90kg, >90kg) and geographic region. In case of rare events for binary endpoints, Fisher's exact test will be used. For repeated measure continuous endpoints, treatment comparisons will be performed using a MMRM model. The MMRM will include treatment, age group (adolescents <18 years and adults ≥18 years), baseline weight, geographic region and baseline value, as explanatory factors. The MMRM model will also include visit, treatment group by visit interaction, and baseline value by visit interaction as additional explanatory factors. The LS mean estimates and their corresponding 95% CI will be provided at each timepoint. In addition, the estimates of LS mean difference and 95% CIs between treatment groups will be provided. Analysis of

covariance will be used to analyze some continuous endpoints when appropriate. The ANCOVA will include treatment group, baseline value, weight, geographic region and age group. The LS mean estimates and their corresponding 95% CI will be provided. In addition, LS mean difference and 95% CIs between treatment groups will be provided. For time to event endpoints, treatment comparisons will be performed using a log-rank test stratified by baseline weight category for adults (≤ 90 kg, >90 kg), geographic region and age group. Kaplan-Meier or life-table estimates of cumulative rate by treatment group will be provided to evaluate the timing of event occurrence in different treatment groups.

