In general, all statistical tests will be performed at a significance level of 0.05 (2-sided) unless otherwise specified. Multiplicity adjustment procedure will be used to control the overall Type I error rate for the primary and key secondary endpoints (section 2.1). No adjustments for multiple comparisons will be made for other secondary endpoints and exploratory endpoints. Nominal p-values for other secondary and exploratory endpoints will be reported but should not be used to infer statistical significance.

The baseline measurement for efficacy endpoints is defined as the closest measurement taken prior to or on the first study agent administration date. The baseline measurement for other endpoints

including safety, PK and immunogenicity is defined as the closest measurement taken prior to the time of the first study agent administration.

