##### From Week 24 Through Week 52 – Randomized Withdrawal and Retreatment Period

###### Randomized Withdrawal period

- The Life table method will be used to estimate the distribution of time to loss of  $\geq 50\%$  of the Week 24 PASI improvement (i.e., time to retreatment) after withdrawal. The median time to loss of  $\geq 50\%$  of the Week 24 PASI improvement will be provided.
- The proportion of PASI responses (PASI 75, 90, and 100) will be summarized over time from Week 24 through Week 52 for participants randomized at Week 24.
- The change and percent change from baseline in PASI total score will be summarized over time from Week 24 through Week 52 for participants randomized at Week 24.

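### For adults re-randomized at Week 24, the continuous-endpoint models omit Week 24 PASI 90 status, a stratification factor, which may make exploratory intervals slightly too wide

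*SAP*

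**What the plan says.** **Design.** Protocol 6.3 re-randomizes adult responders 1:1 at Week 24, and "the randomization will be stratified by geographic region and PASI 90 response status at Week 24".

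**Continuous endpoints.** SAP 4.3.2.3 (Continuous Endpoints) states: "The MMRM will include treatment, age group, baseline weight, geographic region and baseline value, as explanatory factors, if applicable". It adds visit, treatment by visit and baseline by visit. For the alternative model: "The ANCOVA will include treatment group, baseline value, baseline weight, geographic region and age group". Baseline here means Week 0, because SAP 4.1 says: "The baseline measurement for efficacy endpoints is defined as the closest measurement taken prior to or on the first study agent administration date".

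**Reach of that model.** SAP 4.3.2.3 opens by covering both the FAS and the Randomized at Week 24 set. Its rule for intercurrent events extends to the withdrawal period: "Participants experiencing ICEs 1, 2 and 4 (only apply to Week 52 endpoints after retreatment among adult participants". For exploratory endpoints, SAP 4.4.2 says that "the treatment comparisons will be performed using the same analysis methods described in Section 4.3.2.3 for other secondary endpoints". SAP 4.4.2.2 sends withdrawal-period event handling to the same place, and SAP 4.4.2.5 names the endpoint: "The change and percent change from baseline in PASI total score will be summarized over time from Week 24 through Week 52".

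**Other withdrawal analyses.** Protocol 9.3.3 uses region and Week 24 PASI 90 status for Week 52 binary endpoints and for the log-rank tests. SAP 4.3.1.3.1 allows both for PASI 75 at Week 52 and names both for the time-to-loss analyses. For PASI 90 at Week 52 it names region only, since everyone in that analysis is a Week 24 PASI 90 responder.

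**Log-rank wording.** Protocol 9.3.1 (and the synopsis, 1.1) still describes a "log-rank test stratified by baseline weight category for adults", with region and age group as the other strata.

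**The concern.** The withdrawal comparison is a second randomized experiment with its own strata. Continuous endpoints are the only type of withdrawal analysis whose model leaves one of them out. Age group stays in the list although only adults are re-randomized, so it is constant. The closing qualifier in the MMRM sentence can remove a listed factor such as age group, but it cannot add an unlisted one.

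Stratified allocation balances the arms on PASI 90 status and so removes that source of variation from the treatment difference. A model without the factor leaves the same variation in the residual. The reported standard error is then larger than the true one. PASI 90 status at Week 24 is a cut of PASI improvement at Week 24, so it very plausibly predicts PASI change afterwards. At stake is how well the reported intervals are calibrated for these descriptive maintenance results.

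**Working it through.** **1. Size of the set and the plan's power.** 540 adults × 2/3 × 0.75 = 270 re-randomized, or 135 per arm. A pooled two-proportion z test (2-sided 0.05) has power Φ{[Δ − 1.96·√(2p̄(1−p̄)/n)] / √([p₁(1−p₁)+p₂(1−p₂)]/n)}. For 60% vs 80%, this is Φ[(0.200 − 0.109)/0.0544] = 95.2%. For 65% vs 85% it is 97.0%, and for 70% vs 90% it is 98.7%. The plan states 95.2%, 97.0% and 98.6% (Protocol Table 2, SAP Table 9). These concern a binary endpoint and do not depend on the continuous model.

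**2. Analytic size.** Let p be the share of PASI 90 responders and d the stratum effect in residual SDs. Omitting the factor multiplies the reported SE by √(1 + p(1−p)d²). The documents give neither p nor d. An assumed p is 0.59/0.75 ≈ 0.79, which mixes the Week 16 PASI 90 and Week 24 PASI 75 planning rates. Then p(1−p) = 0.1659.

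| d | 1 + 0.1659·d² | interval width ratio |
|---|---|---|
| 0 | 1.000 | 1.000 |
| 0.25 | 1.010 | 1.005 |
| 0.5 | 1.041 | 1.021 |
| 1.0 | 1.166 | 1.080 |
| 1.5 | 1.373 | 1.172 |

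The largest value over p from 0.5 to 0.9 is 1.25 (p = 0.5, d = 1.5).

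**3. Size for percent PASI improvement.** The following are simulations of a single-visit linear model at Week 52 with 270 adults and ICE 4 set to zero improvement. All relapse rates are assumptions.

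*Average relapse on withdrawal 60%, 800 runs.* SE without and with PASI 90 status, by the relapse difference between strata:

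| difference (points) | SE without | SE with | ratio |
|---|---|---|---|
| 0 | 4.335 | 4.314 | 1.005 |
| 20 | 4.484 | 4.382 | 1.023 |
| 30 | 4.546 | 4.379 | 1.038 |
| 40 | 4.595 | 4.348 | 1.057 |

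*Relapse set by stratum, allocation stratified by region and PASI 90 status, 4,000 runs.* Relapse on continued drug is taken as 3% and 10%:

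| relapse, PASI 90 yes / no | ratio, p = 0.79 | ratio, p = 0.65 |
|---|---|---|
| 20% / 30% | 1.036 | 1.048 |
| 30% / 50% | 1.040 | 1.054 |
| 50% / 70% | 1.032 | 1.045 |
| 60% / 60% | 1.013 | 1.018 |

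**4. Fit with the planning rates.** ICE 4 makes a participant a non-responder, so 60% relapse caps Week 52 PASI 75 on withdrawal at 40%, below the planned 60% to 70%. The rows closer to the plan are 20%/30% (average 0.79×20 + 0.21×30 = 22.1%, cap 77.9%) and 30%/50% (0.79×30 + 0.21×50 = 34.2%, cap 65.8%). They give 3.6% to 5.4%. A further run of 1,500 replicates at 35% average relapse gave 0.5% to 5.0%. The range barely moves.

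**5. What the omission does to the estimate itself.** In the 4,000-run check, the actual SD of the estimate is nearly the same with or without the factor:

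| d | model SE / actual SD / coverage, without | model SE / actual SD / coverage, with |
|---|---|---|
| 0 | 0.122 / 0.119 / 95.5% | 0.122 / 0.119 / 95.5% |
| 1.0 | 0.132 / 0.125 / 96.2% | 0.122 / 0.125 / 94.7% |
| 1.5 | 0.143 / 0.124 / 98.1% | 0.122 / 0.123 / 95.3% |

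In the 1,500-run check with 60% relapse, the actual SD was 4.07 in both models at a 40-point difference and 4.18 in both at 20 points. In the stratum-specific relapse scenarios of step 3, coverage without the factor was 95.0% to 95.9%.

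**The case against.** **It may not be a modelled comparison.** SAP 4.4.2.5 says that PASI change will be summarized, whereas elsewhere the SAP speaks of comparing groups when it wants a test. This is arguable. But Protocol 9.3.4 says that exploratory Week 52 comparisons of continued treatment with withdrawal will be performed with nominal p-values, and SAP 4.3.2.3 has an ICE 4 rule for continuous Week 52 endpoints. If any such comparison is fitted, this is the model it gets.

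**It touches nothing that is tested.** This stands. The withdrawal key secondary endpoints are binary or time-to-event. SAP Table 6 lists three binary endpoints and one time-to-event endpoint for adults at Week 52, none continuous. The p-values affected are declared unfit for inference.

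**Stronger readings that a reader might infer:**

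- *The model adjusts only for Week 0 factors.* Region is one of the two re-randomization factors, and it is in the model.
- *Precision worth many participants is lost.* Squaring the largest ratio for percent improvement (1.057² = 1.12) suggests 12% of 270, about 32 people. Step 5 shows otherwise: stratified allocation already delivers that precision to the estimate, and only the reported error is too large.
- *The strata for the two key secondary time-to-loss tests are undecided.* The sentence in Protocol 1.1 and 9.3.1 is leftover general text. Protocol 9.3.3 is specific to the withdrawal period, SAP 4.1 no longer lists weight or age group for the log-rank test, and SAP 4.3.1.3.1 follows 9.3.3.

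**Conclusion.** The omission is real and is inconsistent with the SAP's other withdrawal analyses. Its effect is small and conservative: about 0.5% to 6% of reported interval width for percent PASI improvement, with no bias. Widening occurs only if Week 24 PASI 90 status predicts the outcome beyond the covariates already listed. That is likely but not quantified in the documents. A stratum effect of 1 to 1.5 residual SDs would widen intervals by 8% to 17% at p = 0.79. The sizes come from a single-visit model with assumed relapse rates, so the figure in the full MMRM may differ; the direction does not depend on this. The point is a low-priority clarification worth making because it is free and settles the covariates in advance.

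**What to change.** In SAP 4.3.2.3, add one sentence. For the Randomized at Week 24 set, the MMRM and ANCOVA include PASI 90 response status at Week 24, keep region, baseline value and baseline weight (and, in the MMRM, the visit terms), and omit age group. Refer to it from SAP 4.4.2.2. Adding the endpoint's Week 24 value is optional; under the assumptions tried it gained little beyond the stratum.

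As a consistency edit, change the log-rank sentence in Protocol 1.1 and 9.3.1 to region and Week 24 PASI 90 status, matching Protocol 9.3.3 and SAP 4.3.1.3.1.

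The cost is wording only. Both factors are already recorded for the re-randomization, and no sample size, endpoint or testing order changes.
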